6.4 Safety Analysis

The safety evaluations will focus primarily on AEs and laboratory assessments, but will also include physical examinations, vital signs, ECGs, echocardiograms/MUGA scans and LVEF testing. All subjects included in the As-Treated population will be summarized by treatment arms in the safety analysis.

6.4.1 Treatment-Emergent Adverse Events

Treatment-emergent adverse events will be coded according to the Medical Dictionary for Regulatory Activities (MedDRA) terminology and the severity of the toxicities will be graded according to the NCI CTCAE criteria, v4.03, where applicable.

All TEAEs will be summarized (incidence) and listed by the System Organ Class (SOC), preferred term, toxicity/severity grade, and causal relationship to study medication by treatment arm. In addition, separate

summaries of serious treatment-emergent adverse events (SAEs) and Grade 3 and 4 TEAEs will be presented by treatment arm.

Further, AE tabulations will be repeated using the following subgroups:

- Age Category at Screening (<65 years/>=65 Years)
- Gender (male/female),
- Ethnicity (Asian/Caucasian/Other),
- Region (America and Europe/China All/Asia Other), and
- Lesion Size (<5 cm/>=5cm)
- RFA Dwell Duration (<90, >=90 min)

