14.4 Serious Adverse Events (SAE)

Serious adverse events are defined as any untoward medical occurrences that at any dosage results in one or more of the following:

- Death.
- Is immediately life-threatening, (i.e., presented an immediate risk of death at the time of the adverse event, not an adverse event that hypothetically might have caused death if it were more severe).
- Requires or prolongs inpatient hospitalization.
- Causes persistent or significant disability/incapacity.
- Is a congenital anomaly/birth defect.
- Significant medical event that requires intervention to prevent one of the above outcomes listed in the above definition

Any SAE, which occurs after a subject has signed consent and until Day 28 following last study drug administration, whether or not related to study treatment, must be reported to Pharmacovigilance immediately (within 24 hours of knowledge of the event) via telephone, facsimile or email. If initially reported via telephone or email, this must be followed up by a facsimile of the written SAE report (within 24 hours of the initial telephone report).

Country specific reporting requirements apply. For example, all China local SAEs during the study must be reported within 24 hours to the CFDA.

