14.4.3 Reporting of SAEs

Any serious event, including death from any cause that occurs up to one month following last study treatment administration, whether or not related to the investigational drug or RFA, must be reported to Pharmacovigilance immediately (within 24 hours) via telephone, fax, or e-mail.

If initially reported via telephone or e-mail, this must be followed-up by a written faxed report to be submitted within 24 hours of the initial report.

Pharmacovigilance (SAE) contact phone numbers:

InVentiv Pharmacovigilance

Region	North America	Mainland China	Europe & Rest of World
Fax (SAE reporting)	[REDACTED]	[REDACTED]	[REDACTED]
Email	(NA) [REDACTED] (ROW/Asia Pac)		

Initial Reports

Within 24 hours of the site's knowledge of a serious adverse event:

- Complete a Serious Adverse Event Report Form (SAER), sign it, and fax it to the Pharmacovigilance using the designated fax transmittal form.
- Place the initial version of SAER in the subject's file.

Follow-Up Reports

New information received spontaneously or by request of the Medical Monitor or Safety Surveillance:

Within 48 hours of the receipt of new information:

- Complete a new SAER with the new information. Sign and fax the form to Pharmacovigilance.
- Fax copies of supporting documents (e.g., hospital discharge summaries, lab test results with normal ranges, autopsy or biopsy reports) to Pharmacovigilance.
- Place the follow-up version of the SAE and all supporting documentation in the subject's file.

Final Report

Within 48 hours of the receipt of final information:

- Determine that there is no further information available and this update may be considered final.
- Complete a new SAER form with the new and final information. Sign and fax the form to Pharmacovigilance. As above, send copies of any additional supporting information.
- Place this version of the final SAER into the subject's file.

It is imperative that Pharmacovigilance be informed within 24 hours of a serious adverse experience (including overdose with clinical effect, which is considered an SAE) so that reporting to the FDA and other regulatory agencies can be met within the required time frame (7 or 15 calendar days).

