15.3.2.4 Safety Analyses

The safety evaluations will focus primarily on AEs and laboratory assessments, but will also include physical examinations, vital signs, ECGs, echocardiograms/MUGA scans, hematology, clinical chemistry, and urinalysis beginning at time of signing of informed consent and continuing through Day 28 following study drug administration.. AEs after day 28 visit which are assessed as possibly, probably or definitely related to study treatment will be recorded at any point during the trial. All subjects included in the As-Treated Population will be evaluated by treatment arm in the safety analysis.

Adverse events will be coded according to the Medical Dictionary for Regulatory Activities (MedDRA) terminology and the severity of the toxicities will be graded according to the NCI CTCAE criteria, v4.03, where applicable. Concomitant medications will be coded according to the World Health Organization (WHO) Medication Dictionary for Concomitant Medication.

All AEs will be summarized (incidence) and listed by the System Organ Class (SOC), preferred term, toxicity/severity grade, and causal relationship to study medication. In addition, separate summaries of SAEs and Grade 3 and 4 AEs will be presented.

Hematological and chemistry laboratory parameters will be graded according to the NCI CTCAE v.4.03 criteria, where applicable. Absolute values and changes from baseline will be summarized. In addition, worst severity grade, time to event, and time to resolution will also be summarized.

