5. SAFETY ENDPOINTS

- Adverse events
- Laboratory assessments: hematology including CBC with differential, clinical chemistry, PT/INR, and urinalysis
- Physical Examinations
- Vital signs
- 12-Lead Electrocardiograms (ECGs)
- Echocardiograms/MUGA scans
- LVEF monitoring

Adverse events (AEs) assessment will begin at time of signing informed consent through Day 28 visit following the last study treatment. Adverse events which are assessed as possibly, probably, or definitely related to study treatment will be recorded at any point during the trial and must be followed until resolution or the subject is clinically stable.

Other safety data including physical examinations, vital signs, 12-Lead ECGs, echocardiograms/MUGA scans, LVEF monitoring and hematology, clinical chemistry, and urinalysis will be assessed through Day 28 following study treatment.

To provide surveillance for any late hematologic, cardiac, or liver toxicity, the following additional safety assessments will be done:

- Physical examination, assessment of vital signs, ECGs, CBC with differential, serum chemistry, PT/INR and urinalysis at Month 5, Month 9, and Month 13 or at disease progression, whichever occurs first.
- LVEF monitoring at Month 13 or at disease progression, whichever occurs first
- Serum chemistry and PT/INR assessments at Month 17, Month 21, and Month 25 (+/- 2 weeks) or at disease progression, whichever occurs first.

Subjects with elevated bilirubin levels > 2.0 mg/dL and ≤ 3.0 mg/dL at baseline will return to the clinic on Day 7 for additional safety assessments.

6. STATISTICAL METHODOLOGY**6.1 Statistical and Analytical Issues****6.1.1 Statistical Methods**

Continuous variables will be described in terms of mean, standard deviation, median, minimum, and maximum for each treatment arm. Qualitative variables will be presented in terms of frequency and percent for each treatment arm.

In summary and analysis tables of continuous variables, the minimum and maximum statistics will be presented to the same number of decimal places as the original data. The mean, median, quartiles, and 2-sided 95% confidence interval (CI) will be presented to 1 more decimal place than the original data. The standard deviation and standard error will be presented to 2 more decimal places than the original data.

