6.3 Efficacy Analysis

6.3.1 Primary Efficacy Variable(s)

Overall survival will be measured by time (in months) from randomization to death from any cause or the end of the study. Subjects who have not died will be censored at the date of last study follow-up, or the cut-off date, whichever is earlier as mentioned in Section 3.

The OS cut-off date used for the primary analysis will be based on the observations of the 197th death in the study. All patients dying on the calendar date of the 197th death will be included in the analysis should more than one patient die on the calendar date of the 197th death. Patients having a documented survival status (alive or dead) after this date are censored at the cut-off date.

With the OS cut-off date being event driven, for operational efficiency, the cut-off date for all other study endpoints (e.g., PFS) will be fixed at close proximity of the OS cut-off date, when the milestone is nearing completion. This especially applies to the interim analyses.

OS in the ITT population will be compared between the 2 treatment arms using the stratified log-rank test (Score statistic from PHREG and ties=Breslow (Kalbfleisch and Prentice 1980)). The estimate of the hazard ratio and corresponding 95% CI will be provided using a Cox proportional hazards (CPH) model including treatment and the stratification factors (maximum lesion diameter [3-5 cm versus >5-7 cm] and RFA route [laparoscopic, open surgical, percutaneous]) in the model. The survival curves will be estimated using Kaplan-Meier estimates. The stratification factors will be populated as per the randomization assignment.

Survival for each arm will be summarized using Kaplan Meier curves and is further characterized in terms of the median and survival probability at 12, 24, 36, 48, 60 and 72 months, along with the corresponding 2-sided 95% confidence intervals for the estimates. Confidence intervals for median survival are based upon the methods of (Brookmeyer and Crowley 1982). In addition to Kaplan-Meier estimates, corresponding 2-Sided 95%

confidence intervals constructed using the Clopper-Pearson approximation to the exact binomial proportion (Hollander and Wolfe 1973).

For the first interim analysis, if there are more than 129 events (118+10%), an additional table will be presented for sensitivity purposes, based only on the first 118 events. The same principle applies for the second interim analysis, accordingly.

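### The separate high-grade adverse event summary stops at Grade 4, so that one table can leave out fatal events and favour the arm that has more of them

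*SAP*

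**What the plan says.** The two documents agree. SAP 6.4.1 plans that separate "summaries of serious treatment-emergent adverse events (SAEs) and Grade 3 and 4 TEAEs will be presented by treatment arm". Protocol 15.3.2.4 plans that "separate summaries of SAEs and Grade 3 and 4 AEs will be presented". Neither section mentions Grade 5, uses a Grade 3 or higher category, or names a table of fatal events or of deaths near treatment.

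SAP 6.4.1 also plans a broader table: "All TEAEs will be summarized (incidence) and listed by the System Organ Class (SOC), preferred term, toxicity/severity grade, and causal relationship to study medication", by arm, with no grade left out. On the scale, it says that "the severity of the toxicities will be graded according to the NCI CTCAE criteria, v4.03, where applicable".

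Three other places bear on fatal events:

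- Protocol 14.4 lists death first among the criteria for a serious event.
- Protocol 14.4.3 requires immediate reporting of "Any serious event, including death from any cause that occurs up to one month following last study treatment administration".
- Protocol Appendix V gives adverse event outcome its own code for death.

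**The concern.** A separate high-grade summary draws the most severe events out of a long table broken down by system organ class, preferred term, grade and causality. As worded, this one omits the most severe category. The omission is unequal between arms whenever fatal events are unequal, so the high-grade rates can be closer than they should be, or in the wrong order.

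The protocol itself uses an open-ended category elsewhere. Section 3.3 describes the prior trial's treatment-related events at Grade 3 and above, and Section 6.2.4 describes hyperbilirubinaemia and hepatic failure as grade 3+. A Grade 3 and 4 table would not use the category in which the sponsor reported earlier experience. SAP 6.4.1 also repeats the adverse event tabulations over six subgroup factors, so the omission could carry into those tables.

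**Working it through.** The plan states no figure on this point, so there is none to reproduce. The check is a reading of the text followed by a count illustration.

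**Reading.** Set out by type of subject, with Grade 5 taken as fatal:

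- The only high-grade event was fatal: absent from the Grade 3 and 4 table under any counting rule.
- A fatal event plus a separate Grade 3 or 4 event: absent if subjects are counted once at worst grade, present if every event record is counted.
- A Grade 3 or 4 event and no fatal event: present.

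Neither document says which counting rule applies to adverse events. Worst severity grade is mentioned only for laboratory parameters (SAP 6.4.2 and the laboratory paragraph of Protocol 15.3.2.4).

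**Inputs.** Approximately 550 subjects (Protocol 6.1) randomized 1:1 (Protocol 8.1) give 550/2 = 275 per arm. The safety denominator is the As-Treated population (SAP 2), so 275 is an approximation. All event counts below are assumed. Subjects are counted once at worst grade.

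**Effect of one subject.** 1/275 = 0.36 percentage points.

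**General form.** Let an arm have *t* subjects at Grade 3 or higher, of whom *f* have a fatal event as worst grade. The planned table shows (*t* − *f*)/275; a Grade 3 or higher table shows *t*/275.

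| Grade ≥ 3, arm A vs B | Fatal, A vs B | Grade ≥ 3 rate | Grade 3 and 4 rate |
|---|---|---|---|
| 30 vs 30 | 2 vs 0 | 10.9% vs 10.9% | 28/275 = 10.2% vs 30/275 = 10.9% |
| 30 vs 30 | 5 vs 1 | 10.9% vs 10.9% | 25/275 = 9.1% vs 29/275 = 10.5% |
| 30 vs 30 | 8 vs 2 | 10.9% vs 10.9% | 22/275 = 8.0% vs 28/275 = 10.2% |
| 60 vs 60 | 5 vs 1 | 21.8% vs 21.8% | 55/275 = 20.0% vs 59/275 = 21.5% |
| 32 vs 30 | 5 vs 1 | 11.6% vs 10.9% | 27/275 = 9.8% vs 29/275 = 10.5% |

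The last row shows a reversal. With equal arm sizes, the order flips whenever the difference in fatal counts exceeds the difference in Grade 3 or higher counts; here 5 − 1 = 4 exceeds 32 − 30 = 2.

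**The case against.** The strongest reply is that the same section already reports these events. The all-event table is broken down by grade as well as preferred term and arm, so a fatal hepatic failure would appear under its own term and grade. The sentence that limits the high-grade summary also plans a serious-event summary by arm, and a fatal event is serious by definition. All-cause death from randomization is the primary endpoint, and the data monitoring committee reviews safety regularly. All of this stands.

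It also disposes of a stronger reading that a reader might infer: that treatment-period deaths disappear from the safety report, that the arm with more deaths would look safer overall, or that a hepatic failure signal could be lost entirely. The documents do not support any of these. The distortion is confined to the high-grade summary and any subgroup repeats of it.

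Further points against the concern are also fair:

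- Worst-grade counting is assumed, and the effect is smaller if event records are counted.
- Nothing in the documents supports a particular fatal-event rate. Protocol 3.3 puts treatment-related events of Grade 3 or higher and serious events below 5% in either arm of the prior trial, apart from reversible neutropenia and leukopenia. The largest count assumed above, 8/275 = 2.9%, would be more than half that ceiling if it covers all serious events.
- That prior-trial statement is not the same measure as the planned all-causality table. It shows the sponsor's grade convention and no more.
- SAP 8 puts the list of tables in a separate document, which may include a deaths table.

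These points do not remove the core. The serious-event summary mixes fatal events with hospitalizations and other serious events. Overall survival counts all deaths in the ITT population up to the 197-death cut-off, so it does not describe deaths close to treatment in the As-Treated population. Any separate table list should follow the SAP, and the SAP says Grades 3 and 4.

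**Conclusion.** The point holds, at low severity. Followed as written, both documents produce a high-grade summary that omits subjects whose only high-grade event was fatal and, under worst-grade counting, every subject whose worst grade is 5. That table can favour the arm with more fatal treatment-emergent events and can reverse the order of the arms. Fatal events remain visible by arm elsewhere, but within the planned text they can be separated only through the grade breakdown of the all-event table.

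The size is about 0.36 percentage points per subject dropped. This rests on about 275 subjects per arm and on Grade 5 meaning a fatal event. The total effect cannot be estimated from the documents; the tabulated counts are illustrations.

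**What to change.** In SAP 6.4.1 and Protocol 15.3.2.4, replace the Grade 3 and 4 category with *Grade 3 or higher (Grades 3, 4 and 5), each subject counted once at worst grade*. This matches the category used in Protocol 3.3 and 6.2.4 and settles the unstated counting rule. Add one by-arm table of fatal treatment-emergent events in the As-Treated population, with cause and days from last study treatment. If the separate table list already contains such a table, the SAP need only refer to it.

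The cost is a wording change in two places and one short table. Fatal outcome and deaths up to one month after last treatment are already collected, so no new data are needed.

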6.4.2 Laboratory Parameters

Hematological and chemistry laboratory parameters will be graded according to the NCI CTCAE v.4.03 criteria (see appendix), where applicable. Absolute values and changes from baseline will be summarized by treatment arm at each visit. Shift tables will be provided for the shift from Baseline to the highest post Baseline value. The last on-study value will also be presented (called 'End of Study'), with change from baseline. In addition, worst severity grade, time to event, and time to resolution will also be summarized.

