Post hoc analysis of the PFS and OS data from the HEAT Study suggests that ThermoDox efficacy for the treatment of single lesions is greatly improved when RFA dwell time is \geq 45 minutes. An sRFA treatment for this protocol is defined as the dwell time of \geq 45 minutes measured from the first activation of the RFA probe to produce coagulative necrosis of target tissue through removal of the RFA probe after the final ablation cycle or deployment. This includes the multiple ablation cycles and repositioning time between cycles for an individual patient. Dwell time is relevant for ThermoDox activity because the target tissue and surrounding tissue remain at \geq 40.0°C, even between ablation cycles. This minimum effective dose (MED) of RFA dwell time is achieved by administering 4 ablation cycles. In this trial, all patients will receive the RFA MED of \geq 45 minutes dwell time; in addition, half will be randomized to the ThermoDox MTD of 50 mg/m² and half will be randomized to a dummy infusion of D5W or saline. Randomization and analysis will be stratified by lesion diameter (3-5 cm versus $>$ 5-7 cm) and RFA route (laparoscopic, open surgical, percutaneous). Lesion diameter was found to be a statistically significant prognostic factor in the prior study. Although nearly all subjects in the prior trial (90.7%; 636/701) received percutaneous RFA, this study will also stratify by RFA route for the sake of consistency with the earlier trial's design. Unlike the prior trial, Child Pugh B patients will not be enrolled. They are much more likely than Child Pugh A patients to die from their underlying liver disease, confounding the effect of anticancer treatment (Llovet, et al. 2008). In the HEAT Study, deaths prior to HCC progression occurred at a rate almost five times higher in Child Pugh B patients (19.5%; 8/41) than in Child Pugh A patients (4.1%; 27/660).

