6.2.2 Inclusion Criteria

Subjects must fulfill all of the following inclusion criteria to be eligible to participate in the study.

Subjects may be randomized without a biopsy if they meet American Association for the Study of Liver Disease (AASLD) criteria for the diagnosis of HCC (see Appendix VIII). Subjects not meeting AASLD criteria for HCC will need a biopsy for confirming HCC prior to randomization.

1. Male or female \geq 18 years of age
2. Diagnosed with a single HCC lesion \geq 3.0 cm but \leq 7.0 cm in maximum diameter based on diagnosis at screening.
 - Subjects meeting the AASLD criteria may be randomized without a biopsy, but will undergo a biopsy during the RFA procedure unless contraindicated or unattainable.
 - Subjects not meeting the AASLD criteria for HCC will need a biopsy to confirm HCC prior to randomization.
3. Be an appropriate candidate for receiving RFA as a medically indicated treatment as evaluated by the following factors:
 - The position and accessibility of the target lesion allows for the safe administration of multiple ablation cycles or deployments to achieve a probe dwell time of \geq 45 minutes.
 -
 - Not a candidate for surgical resection according to the local guidelines for resection and in the Investigator's judgment.
4. Child-Pugh Class A without either current encephalopathy or ascites
5. Left ventricular ejection fraction (LVEF) \geq 50%
6. ECOG performance status 0
7. Willing to sign an informed consent form, indicating awareness of the investigational nature of this study that is in keeping with the policies of the institution.

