*** Encephalopathy grades:**

Grade 0: normal consciousness personality, neurological exam and electroencephalogram

Grade 1: restless, sleep disturbed, irritable/agitated, impaired handwriting, 5 cps waves

Grade 2: lethargic, time-disoriented, inappropriate, asterixis, ataxia, slow triphasic waves

Grade 3: somnolent, stuporous, place-disoriented, hyperactive reflexes, rigidity, slower waves

Grade 4: unrousable coma, no personality/behavior, decerebrate, slow 2-3 cps activity

Interpretation:

Child Class A: 5 to 6 points

Child Class B: 7 to 9 points

Child Class C: 10 to 15 points

Source:

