10.2 NCI CTCAE Laboratory Grades

Table 10.2.1 NCI CTCAE V4.03 LAB GRADES

Lab Test	Unit	Grade 1	Grade 2	Grade 3	Grade 4
SERUM CHEMISTRIES + COAGULATION					
Albumin (hypoalbuminemia)	g/dL	[3, LLN)	[2, 3)	[0, 2)	UNDEFINED
Alkaline Phosphatase	units/L	(ULN, 2.5*ULN]	(2.5*ULN, 5*ULN]	(5*ULN, 20*ULN]	>20*ULN
ALT	units/L	(ULN, 3.0*ULN]	(3.0*ULN, 5*ULN]	(5*ULN, 20*ULN]	>20*ULN
AST	units/L	(ULN, 3.0*ULN]	(3.0*ULN, 5*ULN]	(5*ULN, 20*ULN]	>20*ULN
Amylase	units/L	(ULN, 1.5*ULN]	(1.5*ULN, 2*ULN]	(2*ULN, 5*ULN]	>5*ULN
Bilirubin	mg/dL	(ULN, 1.5*ULN]	(1.5*ULN, 3*ULN]	(3*ULN, 10*ULN]	>10*ULN
Calcium max (Hypercalcemia)	mg/dL	(ULN, 11.5]	(11.5, 12.5]	(12.5, 13.5]	>13.5
Calcium min (Hypocalcemia)	mg/dL	[8, LLN)	[7, 8)	[6, 7)	[0, 6)
Cholesterol (Hypercholesterolemia)	mg/dL	(ULN, 300]	(300, 400]	(400, 500]	>500
CK	unit/L	(ULN, 2.5*ULN]	(2.5*ULN, 5*ULN]	(5*ULN, 10*ULN]	>10*ULN
Creatinine	mg/dL	(ULN, 1.5*ULN]	(1.5*ULN, 3*ULN]	(3*ULN, 6*ULN]	>6*ULN
GGT	units/L	(ULN, 2.5*ULN]	(2.5*ULN, 5*ULN]	(5*ULN, 20*ULN]	>20*ULN
Glucose max (hyperglycemia)	mg/dL	(ULN, 160]	(160, 250]	(250, 500]	>500
Glucose min (hypoglycemia)	mg/dL	[55, LLN)	[40, 55)	[30, 40)	[0, 30)
Lipase	units/dL	(ULN, 1.5*ULN]	(1.5*ULN, 2*ULN]	(2*ULN, 5*ULN]	>5*ULN
Fibrinogen	mg/dL	[0.75*LLN, LLN) or decreased from baseline by >0 to 25%	[0.5*LLN, 0.75*LLN) or decreased from baseline by 25 to <50%	[0.25*LLN, 0.5*LLN) or decreased from baseline by 50 to <75%	[0, 0.25*LLN) or decreased from baseline by ≥75% or <50 mg/dL
Magnesium max (Hypermagnesemia)	mg/dL	(ULN, 3]	UNDEFINED	(3, 8]	>8
Magnesium min (Hypomagnesemia)	mg/dL	[1.2, LLN)	[0.9, 1.2)	[0.7, 0.9)	[0, 0.7)
Phosphates (hypophosphatemia)	mg/dL	[2.5, LLN)	[2, 2.5)	[1, 2)	[0, 1)
Potassium max (hyperkalemia)	mEq/L	(ULN, 5.5]	(5.5, 6]	(6, 7]	>7
Potassium min (hypokalemia)	mEq/L	[3, LLN)	UNDEFINED	[2.5, 3)	[0, 2.5)
PT	Seconds	(ULN, 1.5*ULN]	(1.5*ULN, 2.5*ULN]	>2.5*ULN	UNDEFINED
INR		(ULN, 1.5*ULN], >1 - 1.5 times above baseline if on anticoagulation	(1.5*ULN, 2.5*ULN], >1.5 - 2.5 times above baseline if on anticoagulation	>2.5*ULN, >2.5 times above baseline if on anticoagulation	UNDEFINED
PTT	Seconds	(ULN, 1.5*ULN]	(1.5*ULN, 2.5*ULN]	>2.5*ULN	UNDEFINED
Sodium max (hypernatremia)	mEq/L	(ULN, 150]	(150, 155]	(155, 160]	>160
Sodium min (hyponatremia)	mEq/L	[130, LLN)	UNDEFINED	[120, 130)	[0, 120)
Triglycerides (Hypertriglyceridemia)	mg/dL	(150, 300]	(300, 500]	(500, 1000)	>=1000
Uric Acid (hyperuricemia)	mg/dL	(ULN, 10]	UNDEFINED	UNDEFINED	>10

STATISTICAL ANALYSIS PLAN

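### SAP 6.4.2 plans no post-baseline Child-Pugh summary, and its one-test-at-a-time grades and shifts can miss a move from class A to B in subjects near a band edge at entry

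*SAP*

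**What the plan says.** SAP 6.4.2 takes each laboratory test on its own: "Hematological and chemistry laboratory parameters will be graded according to the NCI CTCAE v.4.03 criteria (see appendix), where applicable". It adds "Absolute values and changes from baseline will be summarized by treatment arm at each visit" and "Shift tables will be provided for the shift from Baseline to the highest post Baseline value", together with a last on-study value, worst grade, time to event and time to resolution. SAP 6.4.1 tabulates treatment-emergent adverse events by arm.

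The protocol selects patients on a composite liver measure. Inclusion criterion 4 (Protocol 6.2.2) is "Child-Pugh Class A without either current encephalopathy or ascites", and Appendix I sets "Child Class A: 5 to 6 points" and "Child Class B: 7 to 9 points". In the SAP, Child-Pugh appears only as entry deviation MRD4 in section 6.2.2. No score or class is derived after baseline.

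The components are collected anyway. Protocol Table 1 (note 12) and section 10.1.12 schedule chemistry, which includes bilirubin and albumin, and PT/INR at baseline, Days 14 and 28, and Months 5 to 25 or until progression. Subjects with raised baseline bilirubin have an added Day 7 visit.

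**The concern.** The long-term samples are there to detect delayed liver harm, among other toxicities. The protocol treats Child-Pugh class as the measure that matters for this: section 3.3 explains why class B patients are not enrolled by noting that in the HEAT Study "deaths prior to HCC progression occurred at a rate almost five times higher in Child Pugh B patients (19.5%; 8/41", against 27/660 (4.1%) in class A. If the planned grade bands do not line up with the Child-Pugh cut-offs, a subject can change class while every grade stays the same, and no table would count that subject.

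This matters most for subjects with baseline bilirubin above 2.0 and up to 3.0 mg/dL. Protocol 6.2.4 reports more severe hyperbilirubinemia and hepatic failure in the prior study when baseline bilirubin exceeded 2.0 mg/dL (the excess in hepatic failure was one patient), and it gives the DMC unblinded monitoring of this group. The SAP's adverse event subgroups (6.4.1) do not include baseline bilirubin.

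**Working it through.** The plan states no figure on this point, so the check sets the two sets of cut-offs against each other.

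**Inputs.** Child-Pugh points 1 / 2 / 3 (Protocol Appendix I): bilirubin <2 / 2–3 / >3 mg/dL; albumin >3.5 / 2.8–3.5 / <2.8 g/dL; INR <1.3 / 1.3–1.5 / >1.5. Normal limits (SAP Table 10.1.2): bilirubin upper limit (ULN) 0.012 g/L = 1.2 mg/dL; albumin lower limit (LLN) 33 g/L = 3.3 g/dL. Grades (SAP Table 10.2.1): bilirubin Grade 2 is above 1.5 and up to 3 × ULN; albumin Grade 1 is 3 to below LLN, and Grade 2 is 2 to below 3 g/dL.

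**Step 1, bands.** Bilirubin Grade 2 = 1.5 × 1.2 to 3 × 1.2 = above 1.8 to 3.6 mg/dL, which holds 1, 2 and 3 Child-Pugh points. Normal albumin (3.3 g/dL and above) holds 1 and 2 points. Albumin Grade 2 holds 2 and 3 points.

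**Step 2, the flagged subgroup.** Bilirubin above 2.0 and up to 3.0 mg/dL scores 2. Class A allows at most 6 points and the other four items score at least 1 each, so these subjects enter at exactly 2 + 4 = 6. One more point is class B.

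**Step 3, cases** (items not shown score 1 and do not change, except that the second row has baseline bilirubin in the flagged range, 2 points):

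| Change | Grade | Points | Class |
|---|---|---|---|
| Bilirubin 2.5 to 3.2 mg/dL (2.08 to 2.67 × ULN) | 2 to 2 | 6 to 7 | A to B |
| Albumin 3.6 to 3.4 g/dL | normal to normal | 6 to 7 | A to B |
| Albumin 2.9 to 2.7 g/dL | 2 to 2 | 6 to 7 | A to B |
| Bilirubin 1.9 to 3.5 mg/dL (1.58 to 2.92 × ULN) | 2 to 2 | 5 to 7 | A to B |
| Bilirubin 1.0 to 3.5 mg/dL | 0 to 2 | 5 to 7 | A to B |

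The first four change neither a grade nor a low/normal/high category. The last one is caught.

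**Step 4, dependence on the ULN.** Staying in Grade 2 needs final value / 3 ≤ ULN < initial value / 1.5. For 2.5 to 3.2 that is 1.07 to below 1.67 mg/dL. For 1.9 to 3.5 it is only 1.17 to below 1.27.

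**Step 5, how common on paper.** Take a 0.1-unit grid of bilirubin and albumin with INR at 1 point. Then 208 of 528 eligible class A baselines have some silent route, and all of them have bilirubin above 1.8 mg/dL or albumin 2.8–2.9 g/dL. Of all moves to class B or worse, 25,770 / 639,936 = 4.0% are silent (0.9% to 6.0% with bilirubin ULN 1.0–1.5 and albumin LLN 3.2–3.5). These are grid cells, not patients.

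**Step 6, what the by-visit means would show.** Assume 550 / 2 = 275 per arm and an SD of bilirubin change of 0.5 to 1.0 mg/dL (not given in the documents). The SE of the difference is SD × √(2/275) = 0.043 to 0.085. If an excess share p of one arm moves from 1.9 to 3.5 (a rise of 1.6), the mean difference is 1.6p:
- p = 10%: 0.16 mg/dL, 3.75 to 1.9 SE.
- p = 5%: 0.08 mg/dL, 1.9 to 0.9 SE.

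**Step 7, albumin shift.** The highest later value is a subject's best albumin, so a fall in one sample is hidden whenever any other post-baseline sample is higher.

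**The case against.** A reader might infer that loss of liver function by arm would go unseen. The documents do not support that. SAP 6.4.2 also plans by-visit values and changes from baseline, an end-of-study value and worst grade. SAP 6.4.1 tabulates hepatic events by arm, with all adverse events recorded through Day 28 after the last treatment. An ordinary decline from a normal baseline crosses a grade edge, and the DMC watches the raised-bilirubin subgroup unblinded.

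A reader might also infer a threat to the primary endpoint. The 8/41 and 27/660 figures (ratio 0.195 / 0.041 = 4.8) compare patients by class in the prior trial, as a reason for enrolment policy. They do not show that a later rise in laboratory points carries the same risk. Overall survival counts death from any cause in all randomized subjects, so a missing safety table cannot bias it; the table would only help to interpret it.

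It is also fair to say that no passage promises a post-baseline Child-Pugh analysis, that one-test grading agrees with Protocol 15.3.2.4, and that the table list and DMC charter are separate documents that may hold more. Finally, Child-Pugh INR points can mislead: exclusion 15 exempts therapeutically anticoagulated subjects from the INR limit, and the SAP's grade table allows for this ("ULN, 1.5*ULN], >1 - 1.5 times above baseline if on anticoagulation") where Appendix I does not.

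All of this stands as a limit on the point. It does not remove the gap. Means dilute a change in a few subjects, and grades miss moves within a band. After Day 28, adverse events are recorded only when judged at least possibly related, and physical examinations are listed rather than summarized (SAP 6.4.3). None of these outputs counts subjects who lose class A.

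**Conclusion.** The point holds in limited form. The SAP describes no output that counts change of Child-Pugh class by arm, its grades and shifts can miss a move from A to B, and its shift rule looks at the wrong end for albumin. The exposure is confined to subjects near a band edge at entry, but that includes the raised-bilirubin subgroup, where a single point changes the class. A large decline by arm would still show in the planned tables; a small one might not.

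The conclusion rests on the SAP's standard ranges driving the grades, which section 6.4.2 does not state outright. The albumin 2.9 to 2.7 g/dL case does not depend on them, and the 2.5 to 3.2 mg/dL case survives a wide range of bilirubin limits. The number of patients affected cannot be derived from the documents. This is a worthwhile improvement to safety reporting, not a flaw in the efficacy analysis.

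**What to change.** Add to SAP 6.4.2 one safety table by arm:

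- Derive Child-Pugh points with Protocol Appendix I at baseline and at each scheduled chemistry and PT/INR visit. Label the result as laboratory points only where ascites and encephalopathy are not recorded.
- Report the number of subjects with a rise of 2 or more points and the number moving from class A to B or C, by Day 28 and at any time up to progression. Both counts are needed, because a subject at 6 points changes class with a rise of 1.
- Show this overall and for baseline bilirubin above 2.0 and up to 3.0 mg/dL, with subjects who have a post-baseline sample as the denominator.
- For subjects on anticoagulants, hold INR points at the baseline value or report these subjects separately.
- Use the lowest post-baseline value for the albumin shift.

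The cost is SAP wording and one derived table; no new data are collected. The downside is modest: laboratory-only points can miss clinical ascites or encephalopathy, and scheduled sampling stops at progression, so Day 28 is the cleanest comparison between arms.
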